Specific Aim 3. To determine whether growth hormone therapy-induced changes in fatigue and cognition correlate to changes in the GI microbiome. - mTBI/PASC Baseline (month 0) vs. mTBI/PASC Month 6 – Changes in GI microbiome of mTBI or PASC patients will be correlated to fatigue/cognition symptom resolution in response to growth hormone treatment. Healthy

controls will provide control data. Controls will not receive rhGH treatment. **Outcomes:** Changes in genus, species, Questionnaires (GSRS (GI), MoCA (cognition), BFI and MFSI (fatigue)).

Secondary Aims and Symptom-Related Outcomes and Assessment of Body Composition and Metabolism:

Specific Aim 4a. To determine whether growth hormone therapy alters mood, sleep quality, and quality of life. Mood, sleep, and quality of life will be measured at baseline (month 0) and month 6. (POMS (mood/QOL), QOL-AGHDA (QOL of growth hormone (GH) deficiency), PSQI (sleep), FPQ (food preferences)).

4b. To determine whether growth hormone therapy alters body composition and muscle function. Skeletal muscle mass, as derived from lean body mass determinations, and fat mass will be measured using dual energy x-ray absorptiometry (DEXA) at baseline (month 0) and month 6. (DEXA, Biodex, 6 min walk).

4c. To determine whether growth hormone therapy alters resting energy expenditure. Resting energy expenditure (REE) will be measured using indirect calorimetry at baseline (month 0) and month 6.

Background and Significance

Annually 1.5 million children and adults experience trauma to the head and brain that results in a traumatic brain injury (TBI). While TBI are classified as severe, moderate, or mild based upon the Glasgow Coma Scale (GCS), of the more than 1.5 million people who experience a TBI each year, as many as 90% sustain a mild TBI (mTBI) (1). mTBI can occur during organized sport (football, soccer), home recreation (bike riding, skateboarding), and as a result of a motor vehicle accident or other physical traumatic event. The term 'mild TBI' is misleading as we now know that a significant proportion of mTBI patients suffer from significant impairments or disabilities for many years following the initial brain injury. These include, "foggy brain," short-term memory loss, (1) impaired conversational abilities, and inability to organize daily activities. Together, this symptom complex renders many individuals unable to function in school or maintain a job.

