Notably, the cluster of symptoms associated with post-COVID syndrome include profound fatigue and cognitive dysfunction, which are strikingly consistent with BIAFAC. While studies are underway to understand the details of the mechanism causing BIAFAC and why GH treatment alleviates symptoms in these patients, we are intrigued that the symptom phenotype with post-COVID patients overlaps with many BIAFAC symptoms. It is possible that post-COVID syndrome may be addressed through similar treatment strategies including the potential for prebiotic/probiotic enhancement of microbiome health.

Therefore, in the current study we will assess the GI microbiota in individuals with a history of mTBI or PASC and fatigue. Each participant's baseline will serve as an individual control. An additional and critical control dataset that will be used for comparisons will be provided by analysis of the GI microbiome from healthy controls. Furthermore, we will investigate whether treatment with recombinant Human Growth Hormone (rhGH) will create changes in the gut flora producing microbiomes more similar to those expected in healthy controls and whether these changes correlate with the expected improvements in fatigue, cognition, brain activation, and brain morphology in the mTBI or PASC patients.

Experimental Design and Methods

Enrollment

TBI subjects: To address **AIM 1a** and **AIM 1b** we will study subjects with a history of mild TBI enrolled into either **arm 1** (n=25) or **arm 2** (n=25) for a total of (**n=50**).

Healthy Controls: To address **AIM 1** and **AIM 3** we will study healthy control subjects enrolled into either **arm 1** (n=25) or **arm 2** (n=25) for a total of (**n=50**).

[figure not shown]
PASC subjects: To address **AIM 3** we will study subjects with a history of COVID-19 and PASC symptoms enrolled into **arm 3** (**n=25**).

ARM 1: mTBI and Household Controls

Subjects. We will study subjects (aged 18-70 years) with a history of mild TBI (n=25) and their household controls (aged 18 years and up) (n=25). mTBI subjects will undergo a 6-month intervention of rhGH therapy (See Figure 1). Household controls will be asked to participate in questionnaires, blood draws (amino acid analysis), and fecal sampling (GI microbiome analysis). Household controls will not receive any growth hormone treatment.

mTBI group

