- Perceptual fatigue. Perceptual fatigue will be assessed using the Brief Fatigue Inventory (BFI), a 9-item questionnaire that assesses perceptual fatigue as well as fatigue interferences (e.g. interference with enjoyment of life). The scores from all 9 questions can be average to calculate a Global Fatigue Score, with a range from 0 to 10, with a higher score indicating more fatigue. BFI will be completed at month 0 and month 6 in TBI subjects (24). PASC subjects complete the BFI at months 0, 6, 9 and 12. The Multidimensional Fatigue Symptom Inventory (MFSI) will also be used to measure perceptual fatigue. Fatigue symptoms will be measured using the 30-item Multidimensional Fatigue Symptom Inventory – Short Form, a validated measure that yields one overall score of total fatigue (range -24-96, with higher scores indicating more fatigue) and five subscales (general, physical, emotional, mental, vigor). With the exception of the vigor subscale, higher scores indicate greater fatigue. The MFSI will be measured at month 0 and month 6 in TBI subjects. PASC subjects complete the MFSI at months 0, 6, 9 and 12. If a mTBI subject sustains an additional TBI during the study period, the study will be extended for an additional 6 months. An additional questionnaire will be collected at the end of the 6 month period. If a PASC subject is infected with COVID again during the study months 9 - 12, the study will be extended to collect an additional questionnaires at month 13 and month 15.
- Mood and Quality of Life. Psychological symptoms will be measured in mTBI subjects using the 65-item Profile of Mood States (POMS) questionnaire, a validated measure that yields one overall score of total mood disturbance (range 0-168, with higher scores indicating more disturbance in mood) and six subscales (tension-anxiety, depression-dejection, anger-hostility, vigor-activity, fatigue-inertia, and confusion-bewilderment). With the exception of the vigor-activity subscale, higher scores indicate greater mood disturbance or distress. POMS will be measured at month 0 and month 6 in TBI subjects. PASC subjects complete POMS at months 0, 6, 9 and 12. If a mTBI subject sustains an additional TBI during the study period, the study will be extended for an additional 6 months.

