- Recombinant Human Growth Hormone Administration. mTBI and PASC subjects will be asked to inject themselves with growth hormone daily. The starting dose will be 0.4 mg/day beginning at the baseline study and will increase to 0.6 mg/day when instructed by the study team. The dose increase will happen after the month 1 IGF-1 blood draw and the study team reviews the results and instructs the subject to increase their dose to 0.6 mg/day. TBI subjects will administer growth hormone for 6 months. PASC subjects will administer growth hormone for 9 months. If a mTBI subject sustains an additional TBI during the study period, the study will be extended for an additional 6 months. Genotropin will be provided for the additional 6 months at a dose of 0.6 mg/day.
- Glucagon stimulation test. Arm 3 PASC subjects will have a glucagon stimulation test at month 12. After the IV is placed, 3.5 ml of blood will be collected for the baseline (time: 0 minutes) to test for levels of human growth hormone. 1 mg glucagon (for subjects over 90 kg, 1.5 mg glucagon) will be injected IM in the deltoid muscle of the subject. Additional blood samples (3.5 mL) will be collected to test for levels of human growth hormone at time points: 90 minutes, 120 minutes, 150 minutes, and 180 minutes. All blood samples will be sent to UTMB clinical laboratory for analysis and entered into subjects UTMB medical chart.

Study Procedures for household and healthy control subjects.

Household controls will complete the procedures below. Differences in procedures between Arm 1 and Arm 2 will be noted.

- Vital signs. Vital signs will be collected at all study visits. This will include height, weight, blood pressure, pulse, respirations, and temperature. Vital signs will be recorded on the appropriate study visit CRF.
- Blood draw. Subjects will have blood drawn at the baseline (month 0) and post (month 6) visits. Blood will be drawn using a butterfly needle from a peripheral vein in the arm. Subjects will be fasted for at least 10 hours.
 - Baseline Visit (Month 0):
Up to 15 ml of blood (1 serum separator top (5ml); 1 lithium heparin (6ml); 1 K-EDTA (4ml)) will be collected from fasted (at least 10 hours) subjects for analysis of hormones, amino acids and metabolites. In addition, up to 13ml of blood (1 serum separator top (5ml); 1 lithium heparin (6ml)) will be collected after a standardized meal for the analysis of amino acids.
 - Post Visit (Month 6):

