- Gastrointestinal Symptom questionnaire. Gastrointestinal symptoms will be monitored monthly using the Gastrointestinal Symptom Rating Scale (GSRS). The GSRS is a 15-item questionnaire. Each question has a seven-point Likert-type scale where 1 represents absence of symptoms and 7 represents very troublesome symptoms. The GSRS will be measured monthly.

For Arm 1 only: If the mTBI subject sustains an additional TBI during the study period, the study will be extended for both the mTBI and household control for an additional 6 months. The GSRS will be collected monthly during the 6 month extension.

○

Statistical Considerations

Aim 1a:

In this protocol we intend to compare the GI microbiome of diagnosed mTBI patients against the microbiome of healthy controls (HC). Data will be organized by time (PRE vs. POST) and by treatment (mTBI vs. HC). The hypothesis is that group differences between mTBI and HC will exist at PRE but that GH treatment in the mTBI group will dissolve these differences at POST.

Power calculations using q-PCR data from 22 diagnosed TBI patients and 15 healthy control subjects suggesting that we will be able to detect group differences in genus and/or species in the intestinal flora. These calculations suggest that we would need about 6 subjects per group to have an 80% probability of detecting significant differences in at least one of the previously

identified organisms (two-sided, $\alpha=0.05$). With the proposed subject numbers (25 per group) we calculate that the power would be between 91 – 100 % for at least 8 of the previously identified organisms.

Aim 1b:

Given our recent results from mTBI patients with BIAFAC, that identified two distinct community groups, based upon the presence of specific *Prevotella* species, we require additional participants to achieve group sizes of each type to address differences in the individual species for the pre and post comparisons. Enrollment: We expect to enroll subjects without the need for a HHC to address these differences. These subjects will be compared to matched normal participants from the general population adding 25 TBI and 25 normals to the study creating the power needed to address *Prevotella* positive and negative community types.

[figure not shown]
Aim 2:

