Given the data acquired from two PASC subjects under IRB 20-0361 that have shown indistinguishable profiles to those of BIAFAC communities as well as remarkably reduced GH responses to GST, we expect that the Power calculations explained in this section (above) will also apply to PASC. Because PASC is a recent consequence to the pandemic no data exist to complete Power calculations beyond those of syndromes like BIAFAC that present with similar symptoms. We therefore have proposed enrollment of at least 25 PASC subjects to compare to 25 normal controls already included in this protocol.

For quantifiable (primary) outcomes such as abundances of individual species in the GI microbiome and (secondary) symptom related outcomes, a standard repeated measure ANOVA model will be used. When possible, age and other covariates will be brought into the model to reduce variability and account for random differences between the two groups. Significance tests will be performed at the $\alpha=0.05$ level, and multiple testing corrections will be used to account for potential Type I error rate inflation. Nonparametric, generalized linear, and transformed response models will be considered as necessary to alter the model to account for deviations from standard assumptions (normality, linearity, etc.). Current data support statistical outcomes being established with group sizes similar or slightly larger size than our previous study.

The graph below is based on group difference in *Alistipes onderdonkii*. Power calculations were performed using t-tests with G*Power (two-groups, two-sided, $\alpha=0.05$, Version 3.1.9.2, Germany). Effect size in this case was 1.184.

Below is a list of organisms we identified previously and which were used to conduct the power analyses for the present study. Please note that the intestinal flora includes an incredibly diverse system of organisms and at this time it is difficult to accurately predict which organisms will be included in the biome shifts we expect to see. Therefore, additional organisms may be included in the final microbiome comparisons between mTBI patients and household control subjects. Further power analyses will be conducted using the data collected during this investigation.

Target	n = 20 (10/group)	n=30	n=40	n= 50 (25/group)
Alistipes onderdonkii	70.7%	87.9%	95.4%	98.4%
Desulfovibrio	60.4%	79.3%	89.9%	95.4%
Prevotella spp	97.5%	99.8%	100.0%	100.0%
Akkermansia	64.8%	83.2%	92.6%	96.9%

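### Aims 3 and 4 attribute month 0 to month 6 change to rhGH, but the design supports only change during treatment; the PASC month 9 versus month 12 data could add limited supportive evidence if prespecified

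*Combined protocol and SAP*

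**What the plan says.** Specific Aims states Aim 4a as "To determine whether growth hormone therapy alters mood, sleep quality, and quality of life", and Aims 4b and 4c repeat that form for body composition, muscle function and resting energy expenditure. Aim 3 correlates symptom changes that it describes as induced by therapy with microbiome changes. The contrast given for Aim 3 is month 0 against month 6 within the treated patients, and Aim 4 is measured at the same two visits. The closing paragraph of the therapeutic rationale says that each participant's "baseline will serve as an individual control".

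Statistical Considerations, under Aim 1a, says "Data will be organized by time (PRE vs. POST", crossed with mTBI versus healthy control. After Aim 2 it gives a repeated measures ANOVA for species abundances (primary) and symptom outcomes (secondary), without naming time points. It adds "Significance tests will be performed at the $\alpha=0.05$ level", with multiple-testing corrections.

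For Arm 3, the rhGH administration section says "PASC subjects will administer growth hormone for 9 months", and the fatigue section says "PASC subjects complete the BFI at months 0, 6, 9 and 12". MFSI, POMS, QoL-AGHDA and PSQI follow that schedule. Stool and GSRS are also collected at months 9 and 12. No aim or analysis mentions months 9 or 12.

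**The concern.** The mean change from month 0 to month 6 mixes any drug effect with everything else that happened over six months. mTBI and PASC patients are screened in on a BFI item score of 3 or more, they inject a product they know to be active, and the protocol itself expects improvement. Recovery, expectation and regression to the mean would all push symptom scores in the favourable direction and would be read as drug effect.

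The usual safeguard is a concurrent untreated group of similar patients, and there is none. Without a limit on the claim, a significant pre/post change could be reported as evidence of efficacy. PASC patients do pass from the end of treatment at month 9 to about three months off drug at month 12. With no planned contrast, that comparison can be run, or left out, after the results are seen.

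**Working it through.** **1. The plan's own power figure.** Inputs from Statistical Considerations: "Power calculations were performed using t-tests with G*Power (two-groups, two-sided", α = 0.05; "Effect size in this case was 1.184". For a two-sample t-test the noncentrality is d√(n/2). At 25 per group this is 1.184 × √12.5 = 4.19 with 48 df, giving 98.4%. At 10, 15 and 20 per group the results are 70.7%, 87.9% and 95.4%. All four match the table. They concern patient-versus-control differences in organisms. The documents give no power for Aims 3 or 4.

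**2. What comparison data exist for each outcome.**

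| Outcome | Untreated controls | PASC months 9 and 12 |
|---|---|---|
| BFI, MFSI (Aim 3) | none | yes |
| MoCA (Aim 3) | none | none |
| GSRS, stool (Aim 3) | months 0–6 | yes |
| POMS, PSQI, QoL-AGHDA (Aim 4a) | none | yes |
| FPQ (Aim 4a) | months 0 and 6 | yes |
| DEXA, Biodex, walk (Aim 4b) | none | none |
| REE (Aim 4c) | none | none |

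The controls are household or healthy people not selected for fatigue. mTBI patients, 50 of the 75 treated, have no scheduled off-drug visit.

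**3. How often a pre/post test would mislead.** Suppose the drug does nothing and other causes shift scores by dz standard deviations of change. The values of dz are assumed, since the documents give none. For a paired t-test, two-sided α = 0.05, the noncentrality is dz√n with n − 1 df. The chance of a significant result is:

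| dz (assumed) | n = 25 | n = 50 | n = 75 |
|---|---|---|---|
| 0 | 5% | 5% | 5% |
| 0.2 | 16% | 28% | 40% |
| 0.3 | 30% | 55% | 73% |
| 0.5 | 67% | 93% | 99% |

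The sample sizes are one treated arm, both mTBI arms, and all treated patients. More patients make the misattribution more likely.

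**4. Aim 3 is different.** It tests a correlation between changes. Adding the same constant to every patient's change leaves a correlation unaltered, so step 3 does not apply to that test. What remains is the label: a correlation within treated patients does not show that the drug induced either change.

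**5. What a PASC month 9 versus month 12 contrast could detect.** Paired t-test, two-sided α = 0.05, 80% power:
- 25 completers: the normal approximation is 2.8/√25 = 0.56; the noncentral t gives 0.58 SD of change.
- 21 completers: Arm 1 expects 8 dropouts among 58 (50 + 8), or 13.8%. Borrowing that rate as an assumption, 25 × (1 − 8/58) = 21.6, taken down to 21. The detectable change is 0.64 SD.
- At 90% power: 0.68 and 0.74 SD.
- Bonferroni over five scales (BFI, MFSI, POMS, PSQI, QoL-AGHDA), α = 0.05/5 = 0.01: about 0.73 SD with 25 and 0.81 SD with 21.
- A true reversal of 0.4 SD with 25 completers: power 48% uncorrected, 24% at α = 0.01.

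**The case against.** The single-arm design is in plain view, Aim 4 is labelled secondary, and other passages are hedged, speaking of potential effects and of symptoms that may resolve. Entry requires at least six months since injury or COVID diagnosis, and the protocol describes TBI symptoms lasting many years, so rapid natural recovery is not a given. Selection uses a phone pre-screen while baseline BFI is a separate measurement, which reduces regression to the mean. DEXA and REE are instrument readings not used for selection, and expectation is a weaker explanation there. All of this stands. It bears on how large the bias is, not on whether the design can separate it from a drug effect.

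Three stronger readings are tempting, and the documents do not support them.

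- *A reader might infer that the analysis is confined to PRE versus POST, so months 9 and 12 are discarded.* That sentence belongs to Aim 1a. The repeated measures ANOVA names no time points and does not exclude them. The fair statement is that no contrast is prespecified.
- *A reader might infer that the month 12 data could test Aims 3 and 4 generally.* They cannot reach cognition, Aims 4b and 4c, or any mTBI patient.
- *A reader might want reversal at month 12 as the condition for drug-effect language.* Patients know they have stopped, so expectation alone can produce reversal. The protocol anticipates COVID reinfection in months 9–12, the same window. A real but lasting benefit would show no reversal. Power is also modest, so absence of reversal would often mean nothing.

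**Conclusion.** The concern holds for the causal wording of Aims 3 and 4. Change from month 0 to month 6 in patients who all take rhGH, with no comparable untreated group, shows what happened during treatment and not what the drug caused. The size of the non-drug change cannot be derived from the documents. Over assumed shifts of 0.2 to 0.5 SD, the chance of a falsely attributed significant mean change is 16% to 67% at n = 25 and 40% to 99% at n = 75. For Aim 3 the problem is the therapy-induced label, not inflation of the correlation by a uniform shift.

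The PASC month 9 versus month 12 contrast is worth prespecifying as supportive evidence for questionnaires and stool. It can find a medium-to-large loss of benefit (about 0.58 SD with 25 completers, 0.64 SD with 21, before correction), not a small one. These figures assume a paired t-test at two-sided 5% and, for the 21, that Arm 1's dropout rate carries over. The documents do not call the study open-label; that follows from every patient self-injecting rhGH with no placebo described.

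**What to change.** - Restate Aims 3 and 4 as change during rhGH treatment, with Aim 3 as the correlation between within-patient changes, and limit the conclusions to match.
- For PASC only, name months 0, 6, 9 and 12 in the repeated measures model. Prespecify a supportive month 9 (end of treatment) versus month 12 (off drug) contrast for BFI, MFSI, POMS, PSQI, QoL-AGHDA, GSRS and the main organisms.
- Apply the multiple-testing correction the plan already promises, and add sensitivity analyses for reinfection in months 9–12 and for dropout.
- State in the plan that this contrast is unblinded and uncontrolled, give its detectable change, and say that it cannot address cognition, Aims 4b and 4c, or mTBI patients.
- Do not make reversal, or its absence, a rule for allowing or denying a drug-effect claim.

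The cost is revised wording and one extra analysis on data already scheduled, with no new visits or patients. The downside is a more modest claim.
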